**Overall GVHD Severity**  
(Opinion of the evaluator)

No GVHD     
  Mild     
  Moderate     
  Severe

† Skin scoring should use both percentage of BSA involved by disease signs and the cutaneous features scales. When a discrepancy exists between the percentage of total body surface (BSA) score and the skin feature score, OR if superficial sclerotic features are present (Score 2), but there is impaired mobility or ulceration (Score 3), the higher level should be used for the final skin scoring.

\* Weight loss within 3 months.

\*\*Lung scoring should be performed using both the symptoms and FEV1 scores whenever possible. FEV1 should be used in the final lung scoring where there is discrepancy between symptoms and FEV1 scores.

Abbreviations: ECOG (Eastern Cooperative Oncology Group), KPS (Karnofsky Performance Status), LPS (Lansky Performance Status); BSA (body surface area); ADL (activities of daily living); LFTs (liver function tests); AP (alkaline phosphatase); ALT (alanine aminotransferase); ULN (normal upper limit).

‡ To be completed by specialist or trained medical providers (see Supplemental Figure).

Source:

**Appendix O. NIH Global Severity/Staging of cGVHD****Mild chronic GVHD**

1 or 2 Organs involved with no more than score 1

*plus*

Lung score 0

**Moderate chronic GVHD**

3 or More organs involved with no more than score 1

OR

At least 1 organ (not lung) with a score of 2

OR

Lung score 1

**Severe chronic GVHD**

At least 1 organ with a score of 3

OR

Lung score of 2 or 3

**Key points:**

- In skin: higher of the 2 scores to be used for calculating global severity.
- In lung: FEV1 is used instead of clinical score for calculating global severity.
- If the entire abnormality in an organ is noted to be unequivocally explained by a non-GVHD documented cause, that organ is not included for calculation of the global severity.
- If the abnormality in an organ is attributed to multifactorial causes (GVHD plus other causes) the scored organ will be used for calculation of the global severity regardless of the contributing causes (no downgrading of organ severity score).

**Appendix P. Late Effects Surveillance for Adolescents**

In addition to procedures listed in [Appendix A](#) and [Appendix B](#), adolescents ( $\geq 12$  to  $< 22$  years of age at the time of randomization) will be monitored for growth and development, immune reconstitution, and late effects up to 5 years post randomization.

	Screening	Week 49 $\pm$ 7 days	At month 24, 36, 48, 60 $\pm$ 30 days
Additional measurements			
Height and Weight	X	X	X
Tanner Stage	X	X	X
Immune Reconstitution a Tests		X	X
History of Late Effects (chart review)	X	X	X b

a Immune reconstitution studies will include the following studies obtained as part of standard of care:

- T and B cell enumeration
- Quantitative Immunoglobulins
- Post-vaccination titers

b Are obtained annually. Post vaccination studies may not be performed annually

**Medical Record Review for Transplant-Related Late Effects**

Symptom	No	yes		
		Date of Diagnosis	Was therapy Given?	Was therapy still given at the time this assessment
Diabetes/hyperglycemia requiring chronic treatment				
Hyperlipidemia requiring therapy				
Hypothyroidism requiring hormone replacement				
Gonadal dysfunction requiring hormone replacement (testosterone or estrogen/progesterone)				
Growth hormone deficiency/short stature				
Avascular necrosis				
Osteoporosis				
Osteoporotic fracture				
Depression or anxiety requiring therapy				
Post-traumatic stress disorder requiring therapy				
Cataracts				
Other impairment or disease				
B-cell immune deficiency				
vaccines received over the last year		If vaccines administered complete immunization CRF		

**Tanner Stage****Boys – Development of external genitalia****Stage 1:** Prepubertal**Stage 2:** Enlargement of scrotum and testes; scrotum skin reddens and changes in texture**Stage 3:** Enlargement of penis (length at first); further growth of testes**Stage 4:** Increased size of penis with growth in breadth and development of glans; testes and scrotum larger, scrotum skin darker**Stage 5:** Adult genitalia

**Girls – Breast development****Stage 1:** Prepubertal**Stage 2:** Breast bud stage with elevation of breast and papilla; enlargement of areola**Stage 3:** Further enlargement of breast and areola; no separation of their contour**Stage 4:** Areola and papilla form a secondary mound above level of breast**Stage 5:** Mature stage: projection of papilla only, related to recession of areola**Boys and Girls – Pubic hair****Stage 1:** Prepubertal (can see velus hair similar to abdominal wall)**Stage 2:** Sparse growth of long, slightly pigmented hair, straight or curled, at base of penis or along labia**Stage 3:** Darker, coarser and more curled hair, spreading sparsely over junction of pubes**Stage 4:** Hair adult in type, but covering smaller area than in adult; no spread to medial surface of thighs**Stage 5:** Adult in type and quantity, with horizontal distribution (“feminine”)

**Appendix Q. Corticosteroid-related toxicities and CTCAE preferred terms**

Corticosteroid symptom	CTCAE graded AE
Glucose intolerance related to steroid use	Glucose intolerance
Elevated lipids related to steroid use	Hypertriglyceridemia, Cholesterol high
Hypertension	Hypertension
Steroid myopathy	Generalized muscle weakness
Steroid skin toxicity (eg, striae, thinning of skin, etc.)	Skin atrophy
Neuropsychiatric symptoms including insomnia	Insomnia, Agitation, Psychosis, or other psychiatric symptoms
Oral/vaginal candidiasis or uncomplicated zoster infection	Mucosal infection (e.g. oral/vaginal candidiasis)
Any other infection	Infections
Diabetic nephropathy-related to steroid use	Proteinuria
Posterior reversible encephalopathy	Encephalopathy, Reversible posterior leukoencephalopathy syndrome
Abnormal bone density (>than - 2 Z score)	Osteoporosis (Osteopenia with a t-score -1 to -2.5)
Insufficiency (pathologic) bone fractures	Fracture
Adrenal insufficiency	Adrenal insufficiency
Gastrointestinal perforation	Gastric perforation, Esophageal perforation, Duodenal perforation, Colonic perforation, Ileal perforation
Peptic ulcer disease	Duodenal ulcer
Osteonecrosis of bones (avascular necrosis)	Periodontal disease, Avascular necrosis
Tendon rupture	Musculoskeletal and connective disorders, other
Retinopathy (diabetic or central serous (choroidal) retinopathy)	Retinopathy
Intraocular pressure elevation	Glaucoma, papilledema or eye disorder, other
Posterior subcapsular cataract	Cataract

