##### **1.2.4.5. Infections**

Infections (including sepsis, bacterial, viral, aspergillus or other fungal infections) were observed in subjects treated with ibrutinib therapy. Some of these reported infections have been associated

with hospitalization and death. Consider prophylaxis according to standard of care in subjects who are at increased risk for opportunistic infections (see [Section 6.1](#)). Although causality has not been established, cases of progressive multifocal leukoencephalopathy (PML) have occurred in subjects treated with ibrutinib. Subjects should be monitored for symptoms (fever, chills, weakness, confusion) and appropriate therapy should be instituted as indicated.

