#### **1.2.4.9. Hypertension**

Hypertension has been commonly reported in subjects treated with ibrutinib. Monitor subjects for new onset of hypertension or hypertension that is not adequately controlled after starting ibrutinib. Adjust existing anti-hypertensive medications and/or initiate anti-hypertensive treatment as appropriate.

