#### **Safety**

- Safety and tolerability
- Differences in steroid-related morbidities (eg, hyperglycemia, hypertension)

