### 5.3.1.4. Dose Modification for Adverse Reactions

The dose of ibrutinib/placebo must be modified according to the dose modification guidance in [Table 1](#) and [Table 2](#) if any of the following toxicities occur:

- Grade 4 neutropenia (ANC <500/ $\mu$ L) for more than 7 days. See [Section 6.1](#) for instructions regarding the use of growth factor support
- Grade 3 thrombocytopenia (platelets <50,000/ $\mu$ L) in the presence of clinically significant bleeding events
- Grade 4 thrombocytopenia (platelets <25,000/ $\mu$ L)

- Grade 3 or 4 nausea, vomiting, or diarrhea if persistent, despite optimal anti-emetic and/or anti-diarrheal therapy
- Any other Grade 4 or unmanageable Grade 3 toxicity

Adverse events that are considered related to concomitant high dose corticosteroids (eg, hyperglycemia, insomnia) do not require dose modification or holding of ibrutinib.

For Grade 3 or 4 atrial fibrillation or persistent atrial fibrillation of any grade, consider the risks and benefits of ibrutinib treatment. *If clinically indicated, the use of anticoagulants or antiplatelet agents may be considered for the thromboprophylaxis of atrial fibrillation (Section 6.2.3).*

For other AEs not listed above, including Grade 2 AEs that are deemed per the investigator potentially manageable by dose reduction, these can be managed with a one dose level reduction.

In the event that the investigator feels deviation from the recommendations above is required, please consult the medical monitor to discuss for approval.

If the dose of ibrutinib/placebo is reduced for an adverse event, at the investigator's discretion, the dose of ibrutinib may be re-escalated after 4 weeks of a dose reduction in the absence of a recurrence of the toxicity that led to the reduction. Dose changes must be recorded in the Dose Administration eCRF.

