### **Steroid-related Toxicities**

Treatment-emergent steroid-related AEs will be summarized by the two study arms (Appendix Q). The number and percent of subjects with steroids related TEAEs will be summarized according to intensity (CTCAE, v4.03) and will be categorized by system organ class and preferred term.

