1.2.2. Secondary Endpoints

- Time to withdrawal of all corticosteroids for treatment of cGVHD
- Time to withdrawal of all immunosuppressants, including corticosteroids for treatment of cGVHD (with the exception of ibrutinib/placebo)
- Response rate at 24 weeks
- Improvement in Lee cGVHD Symptom Scale
- Proportion of subjects who achieve reduction of corticosteroids dose level less than 0.15 mg/kg/d at 24 weeks sustained for at least 30 days
- Overall survival (OS)
- Duration of response (DOR)

Safety

- Safety and tolerability of ibrutinib in combination with prednisone compared to prednisone in combination with placebo.
- Differences in corticosteroids -related morbidities (e.g., hyperglycemia, hypertension)

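### The predefined list of steroid toxicities has no hyperglycemia or diabetes mellitus term, although hyperglycemia is the first example in the safety objective it serves

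*Protocol*

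**What the plan says.** Protocol Section 2.2 sets the safety objective as "Differences in steroid-related morbidities (eg, hyperglycemia, hypertension". SAP Section 1.2.2 repeats it with the same two examples in the same order: "Differences in corticosteroids -related morbidities (e.g., hyperglycemia, hypertension". Protocol Section 5.3.1.4 also treats hyperglycemia as a steroid effect: "Adverse events that are considered related to concomitant high dose corticosteroids (eg, hyperglycemia, insomnia".

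The analysis is in Protocol Section 10.5, under Steroid-related Toxicities: "Treatment-emergent steroid-related AEs will be summarized by the two study arms". That paragraph refers to Appendix Q and asks for output by grade, system organ class and preferred term.

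In Appendix Q, the row "Glucose intolerance related to steroid use" is paired with the one term glucose intolerance. Hypertension has its own row. Infections take two rows, one for mucosal candidiasis and uncomplicated zoster and one for "Any other infection". Neither the hypertension row nor the infection rows require a link to steroids.

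SAP Table 3 says that predefined corticosteroid-associated events will be summarized. It neither reproduces a list nor refers to Appendix Q.

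The protocol's account of ibrutinib risks includes both of the broader categories. Section 1.2.4.9: "Hypertension has been commonly reported in subjects treated with ibrutinib". Section 1.2.4.5: "Infections (including sepsis, bacterial, viral, aspergillus or other fungal infections) were observed in subjects treated with ibrutinib therapy".

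**The concern.** A predefined list should contain the events that the objective names. Here the lead example is missing as a term. If a programmer selects events by matching coded terms to Appendix Q, an event reported as hyperglycemia or as diabetes mellitus is not counted in the one table built for this objective. If someone decides at the programming stage to add such terms, the content of a predefined table depends on a choice recorded in neither document. If that choice were made after unblinding, it would be open to the charge of selective reporting.

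There is also a question of interpretation. Hypertension and infection can be caused by prednisone and, on the protocol's own account, by ibrutinib. A steroid-sparing benefit would lower their rates in Arm A, while a direct ibrutinib effect would raise them. An arm difference in those rows therefore does not isolate the effect of lower steroid exposure.

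**Working it through.** The documents state no rate, power or precision for steroid toxicity, so there is no figure of the plan's own to reproduce. The check is a comparison of passages, followed by two illustrations on assumed rates.

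**Passages side by side**

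| Item | In the objective | In Appendix Q | Named as an ibrutinib risk |
|---|---|---|---|
| Hyperglycemia | First example | No such term; nearest is glucose intolerance | Not in Protocol Section 1.2.4 |
| Diabetes mellitus | Not named | No such term; appears only through diabetic nephropathy and diabetic retinopathy | Not in Protocol Section 1.2.4 |
| Hypertension | Second example | Own row, no attribution needed | Yes, 1.2.4.9 |
| Infections | Not named | Two rows, no attribution needed | Yes, 1.2.4.5 |

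Appendix Q thus lists two complications of diabetes but not diabetes itself. The late-effects form in Appendix P does have a combined diabetes and hyperglycemia entry.

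**Illustration 1: the glucose row.** Let the true proportions with a glucose event be p_B and p_A, and let a share f of those subjects be recorded only under hyperglycemia or diabetes terms, the same in both arms. Under literal matching the glucose row shows (1 − f)(p_A − p_B). Assume p_B = 25% and p_A = 15%, a true difference of −10 points:

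- f = 0: −10 points
- f = 0.5: 0.5 × (−10) = −5 points
- f = 1: 0 points

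The documents supply none of these inputs.

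**Illustration 2: an overall count, if one is shown.** Let s be the proportion with a steroid-specific event and i the proportion with an infection, assumed independent. Then P(any) = 1 − (1 − s)(1 − i). Assume s_B = 40% and s_A = 25%, a true difference of −15 points.

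| Infection in Arm B | Difference (A − B), same infection rate in Arm A | Difference (A − B), infection 10 points higher in Arm A |
|---|---|---|
| 30% | 47.5% − 58.0% = −10.5 | 55.0% − 58.0% = −3.0 |
| 50% | 62.5% − 70.0% = −7.5 | 70.0% − 70.0% = 0.0 |
| 70% | 77.5% − 82.0% = −4.5 | 85.0% − 82.0% = +3.0 |

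For example, with 50% infection in Arm B and 60% in Arm A: A = 1 − 0.75 × 0.40 = 70.0%; B = 1 − 0.60 × 0.50 = 70.0%. The separate row for the steroid-specific event still shows −15 points in every case. The dilution therefore affects only an overall count, not the rows by preferred term that the protocol specifies.

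**The case against.** The strongest reply is that little is lost. Protocol Section 10.5 summarizes all treatment-emergent events by system organ class and preferred term, so hyperglycemia will be visible by arm there. SAP Table 3 adds tables of events attributed to corticosteroids or prednisone. Glucose is a central-laboratory parameter (Protocol Section 7.1.2.2), and Protocol Section 10.5 grades all laboratory values. This stands, with two limits. SAP Table 3 restricts graded chemistry to selected parameters, so a glucose table is likely but not promised. The attributed-event tables depend on the investigator's judgement of cause.

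A second reply is that Appendix Q cannot be applied by literal matching at all. Several entries are categories, such as infections or other psychiatric symptoms, and events are coded in MedDRA, so some mapping is unavoidable and might place hyperglycemia under glucose intolerance. That is possible and cannot be settled from the documents. Equally, the SAP states in Section 1 that it supersedes the protocol on endpoint definitions and methods, and its operative list may differ from Appendix Q. Both arguments support writing the list into the SAP.

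A third reply is that hypertension belongs on the list because the objective names it, and that the protocol describes both raised blood pressure and infection as steroid risks (Section 1.3.2). This is correct. Neither group should be removed.

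**Conclusion.** The point holds as a mismatch between a stated objective and the list meant to serve it. Applied as written, Appendix Q leaves hyperglycemia out of the predefined steroid-toxicity table, and the SAP does not repair this. The conclusion assumes that events are selected by the listed terms and that hyperglycemia is not grouped under glucose intolerance in coding. If it were so grouped, the gap for hyperglycemia would close. The size is unknown, because every rate used above is an assumption.

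A reader might go further in three ways that the documents do not support:

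- **That hyperglycemia data are lost.** They are missing from one table and remain in the general adverse event tables.
- **That hypertension and infections are pooled into a composite.** No composite is defined, and the output is by preferred term.
- **That the objective cannot be answered.** The comparison is descriptive, no formal safety test is planned, and the relevant events can be found elsewhere.

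The primary endpoint, the alpha allocation and the sample size are unaffected. The correction is still worth making, because it concerns the first-named example of a stated secondary objective.

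**What to change.** Before unblinding:

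1. Add hyperglycemia and diabetes mellitus terms, coded in MedDRA, to the predefined list of corticosteroid-associated events.
2. Cite that list in SAP Table 3, or attach it, so that the protocol and SAP refer to the same one.
3. Keep hypertension and infections on the list, with a note that the protocol also describes both as ibrutinib risks and that arm differences in those rows are not specific to steroid sparing.
4. If an overall count of subjects with any steroid-related event is presented, give it also without those two groups. This is a choice of presentation, since the plan does not require such a count.

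The cost is a revised term list, a citation and at most one extra table. No new data are needed.

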4. EFFICACY.....	13
5. SAFETY.....	16
6. MODIFICATIONS OF ANALYSIS TO THE PROTOCOL.....	17
7. REFERENCES	18

LIST OF ABBREVIATIONS

Abbreviation	Definition
AE	adverse event
ATC	anatomical therapeutic chemical
cGVHD	chronic graft versus host disease
CI	confidence interval
CIF	Cumulative incidence function
CR	complete response
CTCAE v. 4.03	Common Terminology Criteria for Adverse Events version 4.03
CYP	cytochrome P450
DOR	duration of response
DMC	data monitoring committee
IST	Immunosuppressant treatment
ITT	Intent-to-treat
mITT	Modified intent-to-treat
IWRS	interactive web response system
GVHD	graft versus host disease
MedDRA	Medical Dictionary for Regulatory Activities
NIH	National Institutes of Health
PCYC	Pharmacyclics, LLC
OS	overall survival
PD	progressive disease
PK	Pharmacokinetics
PR	partial response
SAE	serious adverse event
SAP	statistical analysis plan
SD	stable disease
SI	standard international
TEAE	treatment emergent adverse event
ULN	upper limit of normal
WHO	World Health Organization

1. INTRODUCTION

This statistical analysis plan (SAP) is to lay out key elements including definition and statistical methods for analysis of data in evaluation of efficacy and safety for the PCYC-1140-IM study. The SAP specifications including endpoint definitions, order of testing, and methods to be used to analyze the endpoints, supersedes information included in the protocol.

Analyses of biomarker and pharmacokinetics (PK) data are addressed in separate documents.

1.1. Study Design

This is a Phase 3, multicenter, international, randomized, double-blind study of oral ibrutinib in combination with prednisone versus placebo in combination with prednisone in subjects with new onset chronic graft versus host disease (cGVHD).

Approximately 186 subjects with newly diagnosed moderate or severe cGVHD, as defined by the 2014 NIH Consensus Development Project Criteria, were planned to be enrolled. The study enrolled 193 subjects who were randomized in a 1:1 ratio to receive either of the study treatments ibrutinib in combination with prednisone (Arm A) or placebo in combination with prednisone (Arm B).

The randomization between arms was stratified according to:

- Age group (12 to <22 years old vs. ≥ 22 years old)
- NIH Global Severity grade (moderate vs. severe)
- Ongoing use of systemic immunosuppressants that were initiated for either treatment of or prophylaxis for acute GVHD (yes vs. no)

Treatment with the study drug (ibrutinib/placebo) was administered continuously until unacceptable toxicity, progression of the underlying disease, death, or the start of a new systemic treatment for cGVHD. Corticosteroid therapy was tapered as per a standard taper regimen with the goal of reducing exposure to high-moderate dose corticosteroids as quickly as possible according to clinical severity of cGVHD.

Response was assessed according to the NIH Consensus Development Project Criteria (2014).

An independent data monitoring committee (DMC) was established to monitor and review safety and other relevant data on an ongoing basis to ensure the safety of the subjects enrolled in this study and to review results from an interim futility analysis based on data from the first 50 subjects enrolled in the study.

1.2. Endpoints

The primary and secondary endpoints that will be analyzed are listed in this section. Changes from what is outlined in the protocol are described in section 6.

1.2.1. Primary Endpoint

- Response rate at 48 weeks

1.2.2. Secondary Endpoints

- Time to withdrawal of all corticosteroids for treatment of cGVHD
- Time to withdrawal of all immunosuppressants, including corticosteroids for treatment of cGVHD (with the exception of ibrutinib/placebo)
- Response rate at 24 weeks
- Improvement in Lee cGVHD Symptom Scale
- Proportion of subjects who achieve reduction of corticosteroids dose level less than 0.15 mg/kg/d at 24 weeks sustained for at least 30 days
- Overall survival (OS)
- Duration of response (DOR)

Safety

- Safety and tolerability of ibrutinib in combination with prednisone compared to prednisone in combination with placebo.
- Differences in corticosteroids -related morbidities (e.g., hyperglycemia, hypertension)

1.2.3. Exploratory Endpoints

- Improvement in SF-36 patient reported outcome
- Improvement in Karnofsky performance scale score

1.3. Statistical Hypotheses

The primary hypothesis of this study is that the experimental treatment ibrutinib with prednisone compared with placebo with prednisone will significantly improve response rate π at 48 Weeks, as determined by NIH Consensus Development Project Criteria, in subjects with new onset moderate to severe cGVHD.

The statistical hypotheses are as follows:

H_0 : The response rate of the experimental treatment group, $\pi_1(t)$, and the control group, $\pi_C(t)$, are equal at time $t = 48$ Weeks:

H_0 : $\pi_1(t) = \pi_C(t)$, for $t = 48$ Weeks

versus

H_1 : The response rate of experimental treatment group, $\pi_1(t)$, is different from that of the control group, $\pi_C(t)$, at time $t=48$ Weeks:

H_1 : $\pi_1(t) \neq \pi_C(t)$, for $t = 48$ Weeks

These hypotheses will be tested using the chi-square test.

